### **12.7.1.3 Supportive Analysis**

#### **12.7.1.3.1 PP Analysis (Subjects Adherent to the Assigned Product)**

The primary analysis of the “smokers’ health profile” endpoints (see Section 12.7.1.2 “Smokers’ Health Profile Endpoints Evaluation”) will be repeated as a secondary analysis for the PP population (Table 15.2.3.2.2) using a 95% CI and 2-sided p-value. Subjects will be analyzed as randomized by means of a MMRM model including the same adjustment covariates used for the primary analysis (see Section 12.7.1.2 “Smokers’ Health Profile Endpoints Evaluation”), except that randomization arm will be used instead of product use category.

Forest plots of THS 2.2 versus CC arms will be displayed at V7, V10, and V16 for the PP population (Figure 15.1.1.2).

#### **12.7.1.3.2 FAS-AR Sensitivity Analysis**

A sensitivity analysis will be conducted on the “smokers’ health profile” endpoints for the FAS-AR (Table 15.2.3.2.3) using a 95% CI and 2-sided p-value to compare the THS 2.2 and CC arms. Subjects will be analyzed as randomized by means of a MMRM model including the same adjustment covariates used for the primary analysis (see Section 12.7.1.2 Smokers’ Health Profile Endpoints Evaluation”), except that randomization arm will be used instead of product use category. The FAS-AR results will be interpreted taking into account those observed from the sensitivity analysis described in Section 12.7.3.2 “Exposure/Response and Effect of Dual-Use on Smokers’ Health Profile”.

Forest plots of THS 2.2 versus CC arms will be displayed at V7, V10, and V16 for the FAS-AR (Figure 15.1.1.3).

#### **12.7.1.3.3 FAS-EX Supportive Analysis**

A supportive analysis will be conducted on the “smokers’ health profile” endpoints for the FAS-EX (Table 15.2.3.2.1) to compare the Dual-use versus CC-use at V7, V10, and V16. Subjects will be analyzed by means of a MMRM model including the same adjustment covariates used for the primary analysis (see Section 12.7.1.2 Smokers’ Health Profile

Endpoints Evaluation”). The estimates of the difference/percent reduction (and 2-sided p-values) will be presented together with 95% CI for Dual-use vs CC-use and also displayed as forest plots at V7, V10, and V16 (Figure 15.1.1.1) for the FAS-EX population.

#### **12.7.1.3.4 Missing Product Use Sensitivity Analysis**

A Missing product use sensitivity analysis will be produced for the FAS-EX population using a 95% CI and 2-sided p-value to compare THS-use versus CC-use, by re-analyzing the primary endpoints re-classifying all subjects based on the available data in the diary (Table 15.2.3.1.2) with no imputation (see Section 16.3.2).

#### **12.7.1.3.5 Sensitivity Analysis for Subjects Enrolled into Extension**

##### **Study**

A sensitivity analysis will be produced for the subset of FAS-EX subjects who enrolled into the extension study using a 95% CI and 2-sided p-value to compare THS-use versus CC-use and Dual-use vs CC-use (Table 15.2.3.1.3).

#### **12.7.1.3.6 Multiple Imputation Sensitivity Analysis**

A multiple imputation sensitivity analysis will be conducted on the “smokers’ health profile” endpoints for the FAS-EX (Table 15.2.3.1.4) using a 95% CI and 2-sided p-value to compare THS-use versus CC-use at Months 6 and 12. The analysis will only be performed for endpoints which have more than 10% missing data at baseline or Month 12 for those in the FAS-EX population.

First, missing data will be imputed separately for each product use category (JV4, V16) using the Markov Chain Monte Carlo multiple imputation method with terms including baseline value, Month 3 value, Month 6 value, Month 12 value, sex, Caucasian origin, and the same adjustment covariates for each specific clinical risk endpoint as included in the primary analysis. For log-transformed parameters, log-transformed values will be used during imputation.

Then, for each imputed dataset, adjusted LS means and CIs will be determined from a mixed effects model conducted on original Month 6 or Month 12 values with baseline value, sex, Caucasian origin, product use pattern category (Month 6 or Month 12), and other baseline covariates relevant for each specific clinical risk endpoint as fixed effect factors and site as a random effect. For log-transformed parameters, log-transformed values will be used in the model, and adjusted geometric LS means and CIs will be determined.

Finally, the results across imputations are combined to produce final inferential estimates. In case of model convergence issues, this will be reported in the study report and additional covariance structures will be investigated with the following order: heterogeneous compound symmetry (type=csh), heterogeneous toeplitz (type=toeph), heterogeneous autoregressive (1) (type=arh(1)), and variance components (type=vc).

### **12.7.1.3.7 Sensitivity Analysis for Derived Endpoints Including LLOQ Values in Denominator**

A sensitivity analysis will be produced for the 24-hour urine creatinine-adjusted “smokers’ health profile” endpoints in which derived values will be calculated using half LLOQ creatinine values for the denominator in cases where the creatinine value is below LLOQ. This sensitivity analysis will be performed for the FAS-EX population using a 95% CI and 2-sided p-value to compare THS-use versus CC-use and Dual-use vs CC-use (Table 15.2.3.1.5).

### **12.7.1.3.8 Descriptive Analysis of Primary Endpoints**

The primary endpoints of the “smokers’ health profile” (HDL-C, WBC, sICAM-1, 11-DTXB2, 8-epi-PGF2 $\alpha$ , COHb, FEV1, Total NNAL) will be summarized as detailed in Section 12.1.3 “Descriptive Statistics” for the FAS-EX, FAS-AR, and PP Populations (Tables 15.2.4.1.\*). The primary endpoints will also be summarized by sex and average daily CC consumption at V1 for the FAS-EX (Tables 15.2.4.1.1.\*).

The listing of the urinary clinical risk endpoints and BoExp will include the concentration adjusted for creatinine and the percent change from Baseline in the concentration adjusted for creatinine (Listings 15.3.3.1-15.3.3.3).

The listing and summary of the COHb data will include the concentration, the percent change from Baseline in the levels, and a flag for whether a subject’s COHb was <2%. The listing of CO will flag subjects with CO level > 10 ppm.

## **12.7.2 Secondary Analyses**

### **12.7.2.1 Product Use**

The number of CC or THS Tobacco Sticks used daily (as reported on the self-reported product use electronic diary) will be described on the FAS-EX (for both 6-month and 12-month product use categories) and PP population and on the Safety Population. Summaries will include product use of other nicotine/tobacco-containing products and overall tobacco product grouping CC, THS Tobacco sticks, and other tobacco product (Listings 15.3.2.1-15.3.2.3; Tables 15.2.2.1.1-15.2.2.1.3 and 15.2.2.1.1.1). Summaries will also be presented by

sex and average daily CC consumption at V1 for the 12-month product use categories for the FAS-EX (Tables 15.2.2.1.1.2 and 15.2.2.1.1.3). In addition, summaries will be presented for the 6-month product use categories for the FAS-EX (15.2.2.1.1.4).

Product use data will be summarized by the monthly exposure period by study arm on the Safety Population (Table 15.2.2.1.3.1).

In addition, the number and percent of subjects in each product use pattern category will be summarized in 6-month intervals (J[V4, V10], [V10, V16]) and in 12-month interval (J[V4, V16]) for the FAS-EX, Safety, and FAS-AR populations (Tables 15.2.5.1-15.2.5.3). Summaries will also be presented by sex and average daily CC consumption at V1 for the FAS-EX (Tables 15.2.5.1.1 and 15.2.5.1.2). In addition, a summary of detailed product use patterns will be produced for the FAS-EX (Table 15.2.5.4).

The distribution of product use will also be summarized for the THS-use, Dual-use, and CC-use by cross-tabulation of the frequency (number and percent) of subjects for the categories of the following two variables for the FAS-EX population (Table 15.2.4.15):

- Average number of daily CC smoked over the 12 month period.
- Average number of daily THS Tobacco Sticks used over the 12 month period.

Categories will be defined as “<1”, “1-4”, “5-10”, “11-20”, “21+”.

### **12.7.2.2 Reduction of Exposure to Biomarker of Exposure**

The level of the BoExp (CO, Total NNN) and their percent change from Baseline will be listed and summarized at V7, V10, and V16 (Listings 15.3.3.1, 15.3.3.2, and 15.3.3.3.1; Tables 15.2.4.2.1-15.2.4.2.3). All BoExp parameters will be log-transformed except CO.

The reduced exposure will be demonstrated if a statistically significant reduction of biomarkers level in THS-use compared to CC-use are observed. To this aim, the MMRM analysis approach adopted in Section 12.7.1.2 “Smokers’ Health Profile Endpoints Evaluation” will be used on log-transformed Total NNN to compare the geometrical means ratio between THS-use and CC-use at V7, V10, and V16, using a 5% Type I error with no adjustment for multiplicity (Tables 15.2.3.3.1-15.2.3.3.3). Exhaled CO will be analyzed on the original scale and test the LS mean difference between THS-use and CC-use at V7, V10, and V16. The models will include the same adjustment covariates used for the primary analysis of COHb and Total NNAL. Site will be included as a random effect. The ratios/differences will also be compared for Dual-use versus CC-use, using a 5% Type I error. The estimates of the difference/percent reduction will be presented together with 95% CI for THS 2.2 versus CC arms for the FAS-AR and PP populations.

All summaries and analysis will be produced for the FAS-EX, FAS-AR, and PP populations.

In addition, a sensitivity analysis will be produced for the Total NNN creatinine-adjusted endpoint in which the derived values will be calculated using half LLOQ creatinine values for the denominator in cases where the creatinine value is below LLOQ. This sensitivity analysis will be performed for the FAS-EX population to compare THS-use versus CC-use and Dual-use vs CC-use (Table 15.2.3.3.1.1).

### **12.7.2.3 Nicotine Exposure**

The level of Neq in 24-hour urine adjusted for creatinine, Nicotine and Cotinine in plasma will be listed and summarized over time (Listings 15.3.3.4 and 15.3.3.4; Table 15.2.4.3.\*).

The MMRM analysis approach adopted in Section 12.7.1.2 “Smokers’ Health Profile Endpoints Evaluation” will be used on log-transformed Neq in 24-hour urine adjusted for creatinine, Nicotine, and Cotinine levels to compare the geometrical means ratio between THS-use and CC-use at V7, V10, and V16, using a 5% Type I error with no adjustment for multiplicity. The models will include the same adjustment covariates used for the primary analysis of COHb and Total NNAL. Site will be included as a random effect. The geometrical mean ratios will also be tested for Dual-use versus CC-use, using a 5% Type I error. The estimates of the percent reduction will be presented together with 95% CI for THS 2.2 versus CC arms. All summaries and analysis will be produced for the FAS-EX, FAS-AR, and PP population (Tables 15.2.4.4.\*).

In addition, a sensitivity analysis will be produced for the Neq creatinine-adjusted endpoint in which the derived values will be calculated using half LLOQ creatinine values for the denominator in cases where the creatinine value is below LLOQ. This sensitivity analysis will be performed for the FAS-EX population to compare THS-use versus CC-use and Dual-use vs CC-use (Table 15.2.4.4.1.1).

### **12.7.2.4 Change in biological and functional markers**

#### **12.7.2.4.1 Lung Function and Cardiovascular diseases markers**

Lung function and Cardiovascular data will be collected at V3, V7, V10, and V16.

Lung function data includes spirometry (FEV1, FVC, FEV1/FVC, FEF 25-75, and bronchodilator reversibility in FEV1) and lung volume data (FRC, VC, TLC, IC and RV), and the brand (trade) name and dose of the bronchodilator. Spirometry data will also be collected at V1. At V1, V10, and V16, pre and post-bronchodilator spirometry test will be conducted, while at V3 and V7 only post-bronchodilator test will be performed. Spirometry predicted values will be standardized to the National Health and Nutrition Examination

Survey III predicted set [21], using the formula by Hankinson et al. [22]. Predicted values for Lung function parameters will be derived by a central provider.

Cardiovascular data include the following:

- MPO, Apo A1 and Apo B, Apo B/Apo A1, LDL-C, hs-CRP in serum.
- Fibrinogen, and homocysteine in plasma.
- Platelet count, and HbA1c in whole blood.
- Albumin in urine (expressed as concentration adjusted to creatinine and as quantity excreted in 24h).
- Blood Pressure, weight, waist circumference.

The level of biological and functional markers and their change from Baseline will be listed, and summarized at V7, V10, and V16 (Listings 15.3.3.1-15.3.3.3, 15.3.6.9, and 15.3.6.11; Tables 15.2.4.5.1-15.2.4.5.3, and 15.2.4.7.1-15.2.4.7.3). RV will be summarized descriptively only. FEV1 %pred (post-bronchodilator) will not be analyzed or presented descriptively with the other lung function data since it is already summarized as a primary endpoint. Albumin in urine expressed as quantity excreted in 24h will be listed only.

The MMRM analysis approach adopted in Section 12.7.1.2 “Smokers’ Health Profile Endpoints Evaluation” will be used to compare between THS-use and CC-use at V7, V10, and V16, using a 5% Type I error with no adjustment for multiplicity. Lung function data, apart from RV and FEV1 %pred (post-bronchodilator), will be analyzed in the original scale (Tables 15.2.4.6.1-15.2.4.6.3 and 15.2.4.8.1-15.2.4.8.3), and cardiovascular data will be analyzed in original scale for Apo A1, Apo B, Apo B/Apo A1, LDL-C, HbA1c, blood pressure, weight, and waist circumference, and in logarithmic scale for albumin in urine (expressed as concentration adjusted to creatinine), MPO, hs-CRP, fibrinogen, homocysteine, and platelet count.

The models will only include terms for visit, sex, Caucasian origin, age, smoking intensity, baseline level, product use pattern category, and the interactions of visit with both baseline level and product use category. Site will be included as a random effect. The ratios/differences will also be compared for THS-use versus CC-use and Dual-use versus CC-use, using a 5% Type I error. The estimates of the difference or ratio/percent reduction will be presented together with 95% CI. These estimates will be produced for THS 2.2 versus CC arms for the FAS-AR and PP populations.

All summaries and analyses will be performed on the FAS-EX, FAS-AR, and PP populations.

In addition, a sensitivity analysis will be produced for the albumin in urine creatinine-adjusted endpoint and the Apo B/Apo A1 endpoint in which the derived values will be calculated using half LLOQ values for the denominator in cases where the value is below LLOQ. This sensitivity analysis will be performed for the FAS-EX population to compare THS-use versus CC-use and Dual-use vs CC-use (Table 15.2.4.8.1.1).

### 12.7.2.5 Cough Symptoms

Cough symptoms will be assessed by means of the cough questionnaire, as described in Section 7.2.8 “Cough Questionnaire”.

Descriptive analysis for change from Baseline will be presented for the VAS score and evaluating the level of cough bother at V7, V10, and V16. For the calculation of the change from Baseline, missing VAS values will be imputed with zero when no cough was reported.

The responses to the individual items, including the VAS score, change from Baseline, 3 Likert scales measuring the intensity and frequency of cough, and the amount of sputum production will be listed and summarized using the number of subjects who reported to experience cough as denominator (Listings 15.3.3.5; Tables 15.2.4.9.1 and 15.2.4.9.2).

The number and percentage of subjects reporting a cough will be summarized by randomization arm and product use pattern categories.

The answers to the open question related to any other important observation will be listed.

In addition, a logistic mixed-effects regression model for repeated measures will be used to compare the percentages of subjects reporting the need to cough between THS-use and CC-use at V7, V10, and V16 (Table 15.2.4.10). The model will include terms for visit, sex, Caucasian origin, age, smoking intensity, baseline cough, product use pattern category, and the interactions of visit with both baseline cough and product use category. Site will be included as a random effect. The point and 95% CI of LS means of the proportion of subjects reporting need to cough and their odds ratio will be presented for THS-use versus CC-use and also for Dual-use versus CC-use.

The SAS code for the logistic regression model to be used is shown below:

```
Proc glimmix data=_data_ method=rspl maxopt=200;
Class subject baseline product_use site sex caucasian_origin
visit;
Model endpoint = baseline sex caucasian_origin age
smoking_intensity product_use visit baseline*visit
product_use*visit / dist=binary link=logit ddfm=kr;
```

```
Random site;  
Random visit / subject=subject type=un residual;  
Lsmeans product_use*visit / slice=visit alpha=0.05 diff cl  
pdiff ilink or;  
Run;
```

In case of model convergence issues, this will be reported in the study report and additional covariance structures will be investigated with the following order: heterogeneous compound symmetry (type=csh), heterogeneous toeplitz (type=toeph), heterogeneous autoregressive (1) (type=arh(1)), and variance components (type=vc). All descriptive summaries will be performed on the FAS-EX and PP populations and the logistic regression will be performed on the FAS-EX.

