### 7.2.8 Cough Questionnaire

Subjects will self-report the respiratory symptom ‘cough’ using a visual analog scale (VAS), three Likert scale questions, and one open ended question at V3, V7, V10, and V16.

Subjects will be asked if they have experienced a regular need to cough, (*i.e.*, whether they have coughed several times in the previous 24 hours prior to assessment). If the answer is ‘yes’, subjects will be asked to complete the questionnaire.

The VAS will assess how bothersome cough is to the subject ranging from ‘not bothering me at all’ to ‘extremely bothersome’, and this will be given a numeric value between 0 and 100, measured on a 100 mm scale.

Subjects will also be asked to assess the intensity and frequency of cough and the amount of sputum production on Likert scales as presented in Table 11.

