Table 15.2.4.8.3	Analysis of Additional Cardiovascular Disease Markers – FAS-AR			
Table 15.2.4.9.1	Summary of Cough Assessment Over Study – FAS-EX			
Table 15.2.4.9.2	Summary of Cough Assessment Over Study – PP Population			
Table 15.2.4.10	Analysis of Proportion of Subjects Reporting Need to Cough Over Study – FAS-EX			
Table 15.2.4.11.1	Descriptive Statistics of MCEQ Subscales – FAS-EX			
Table 15.2.4.11.2	Descriptive Statistics of MCEQ Subscales – PP Population			

Table No.	Title	Topline (Y/N)	Safety (Y/N)	Clinical Trial.gov (Y/N)
Table 15.2.4.12.1	Analysis of MCEQ Subscales – FAS-EX			
Table 15.2.4.12.2	Analysis of MCEQ Subscales – PP Population			
Table 15.2.4.13.1	Descriptive Statistics of FTND Results – FAS-EX			
Table 15.2.4.13.2	Descriptive Statistics of FTND Results – PP Population			
Table 15.2.4.14.1	Descriptive Statistics of Intent to Use THS 2.2 Questionnaire – FAS-EX			
Table 15.2.4.14.2	Descriptive Statistics of Intention to Use THS 2.2 Questionnaire – PP Population			
Table 15.2.4.15	Descriptive Statistics of Distribution of Dual Use over Randomized Exposure Period – FAS-EX			
Table 15.2.4.16	Analysis of Final Propensity Model – FAS-AR			
Table 15.2.4.17	Analysis of Exposure-Response Relationship of Dual Use – FAS-AR			
Table 15.2.5.1	Summary of Product Use Pattern – FAS-EX	Y		

Table No.	Title	Topline (Y/N)	Safety (Y/N)	Clinical Trial.gov (Y/N)
Table 15.2.5.1.1	Summary of Product Use Pattern by Sex - FAS-EX			
Table 15.2.5.1.2	Summary of Product Use Pattern by Consumption Level - FAS-EX			
Table 15.2.5.2	Summary of Product Use Pattern - Safety Population			
Table 15.2.5.3	Summary of Product Use Pattern - FAS-AR	Y		
Table 15.2.5.4	Summary of Detailed Product Use Pattern - FAS-EX			
Table 15.2.6.1	Summary of Adverse Events – Safety Population		Y	
Table 15.2.6.2	Summary of Adverse Events by Product Use Pattern Category – Safety Population	Y	Y	
Table 15.2.6.3	Summary of Adverse Events by System Organ Class and Preferred Term – Safety Population		Y	
Table 15.2.6.3.1	Summary of Monthly Adverse Events by System Organ Class and Preferred Term – Safety Population		Y	
Table 15.2.6.4	Summary of Adverse Events by Product Use Pattern Category, System Organ Class and Preferred Term – Safety Population	Y	Y	

Table No.	Title	Topline (Y/N)	Safety (Y/N)	Clinical Trial.gov (Y/N)

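### The model-based cough proportions in Table 15.2.4.10 weight baseline coughers and non-coughers equally, so they are not adjusted cough proportions for FAS-EX (a minor correction; the odds ratio is unaffected)

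*SAP*

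**What the plan says.** SAP section 12.7.2.5 fits a repeated-measures logistic mixed model to the need to cough on FAS-EX, with site as a random effect. Its stated output is: "The point and 95% CI of LS means of the proportion of subjects reporting need to cough and their odds ratio will be presented". Two contrasts are planned, each with CC-use as the reference: one for THS-use and one for Dual-use. The matching entry in SAP section 16.4, Table 15.2.4.10, is titled "Analysis of Proportion of Subjects Reporting Need to Cough Over Study".

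Four parts of the specification decide what those proportions are:

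- The baseline item is yes/no. SAP section 7.2.8: "Subjects will be asked if they have experienced a regular need to cough".
- That item is declared categorical, with sex and Caucasian origin: "Class subject baseline product_use site sex caucasian_origin". All three are fixed effects: "Model endpoint = baseline sex caucasian_origin age".
- The only interactions are "the interactions of visit with both baseline cough and product use category". There is no product use by baseline cough term.
- The LS means request is "Lsmeans product_use*visit / slice=visit alpha=0.05 diff cl", continued as "pdiff ilink or". It has no observed-margins option and sets no other weights.

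SAP section 9 replaces the protocol's incidence-rate differences (protocol section 12.6.2) with odds ratios and drops p-values for this analysis. Section 12.7.2.5 also plans the number and percentage reporting a cough by randomization arm and by product use category.

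**The concern.** By default, LSMEANS gives every level of the other class effects equal weight. With baseline cough in CLASS, half the weight goes to baseline coughers whatever their share of FAS-EX. The averaging is done on the logit scale and only then inverse-linked. No part of the SAP sets other weights or says that the values refer to balanced covariate levels, so a reader of Table 15.2.4.10 will take them as adjusted FAS-EX cough rates.

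With incidence-rate differences removed, these proportions are the only model-based absolute measure of cough, which belongs to secondary objective 5. Any adjusted absolute gap between THS-use and CC-use would have to be read from them.

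**Working it through.** The documents give no cough rates, so there is no figure of the plan's own to reproduce, and **every rate below is an assumption**. For clarity, only baseline cough is carried as a covariate.

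**Notation.** b is the baseline cough prevalence in FAS-EX. p1 and p0 are the CC-use probabilities of cough at V16 in baseline coughers and non-coughers. OR is the THS-use versus CC-use odds ratio.

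**Formulas for CC-use** (for THS-use, add ln OR to each logit):

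- Printed code: expit(0.5·logit p1 + 0.5·logit p0)
- Observed margins (OM): expit(b·logit p1 + (1−b)·logit p0)
- Standardised to FAS-EX: b·p1 + (1−b)·p0

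**Worked case: b = 0.20, p1 = 0.60, p0 = 0.10, OR = 0.6.**

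- logit 0.60 = 0.405, logit 0.10 = −2.197, ln 0.6 = −0.511.
- LS mean, CC-use: expit((0.405 − 2.197)/2) = expit(−0.896) = 29.0%.
- LS mean, THS-use: expit(−0.896 − 0.511) = expit(−1.407) = 19.7%.
- Standardised, CC-use: 0.20 × 0.60 + 0.80 × 0.10 = 20.0%.
- THS-use probabilities: odds 1.5 × 0.6 = 0.9 give 0.474, and odds 0.111 × 0.6 = 0.0667 give 0.0625.
- Standardised, THS-use: 0.20 × 0.474 + 0.80 × 0.0625 = 14.5%.
- OM, CC-use: expit(0.20 × 0.405 − 0.80 × 2.197) = expit(−1.677) = 15.8%.

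**Same p1, p0 and OR with b varied** (CC-use / THS-use; last column is LS mean minus standardised, CC-use):

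| b | LS means, printed code | Standardised | OM | CC-use error |
|---|---|---|---|---|
| 10% | 29.0% / 19.7% | 15.0% / 10.4% | 12.6% / 8.0% | +14.0 points |
| 20% | 29.0% / 19.7% | 20.0% / 14.5% | 15.8% / 10.1% | +9.0 points |
| 30% | 29.0% / 19.7% | 25.0% / 18.6% | 19.5% / 12.7% | +4.0 points |
| 40% | 29.0% / 19.7% | 30.0% / 22.7% | 23.9% / 15.9% | −1.0 point |
| 50% | 29.0% / 19.7% | 35.0% / 26.8% | 29.0% / 19.7% | −6.0 points |

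The LS means do not move with b. The LS-mean gap stays at 9.3 points, against standardised gaps of 4.6, 5.5, 6.4, 7.3 and 8.2 points.

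**The gap can also be too small.** With b = 0.40, p1 = 0.40, p0 = 0.02 and OR = 0.6, the LS means are 10.4% and 6.5% (gap 3.9 points). The standardised values are 17.2% and 12.2% (gap 5.0 points).

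**Check by model fit.** A logistic model was fitted to 200,000 simulated subjects with b = 0.25, p0 = 0.15, p1 = 0.65 and OR = 0.70. It gave default LS means of 36.5% and 28.7%, against observed proportions of 27.5% and 22.5%. The fitted odds ratio was 0.70.

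**Odds ratio.** With no product use by baseline cough term, the log odds ratio is the same at both baseline levels. Any weighting of the two levels returns the same value.

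**The case against.** The strongest defence has four parts.

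1. **The planned contrast is sound.** The comparison is the odds ratio, which the weighting does not touch. The SAP plans no difference in proportions. This stands.
2. **Observed rates are available.** Crude percentages by arm and product use category are in the same section. This also stands, although they are unadjusted. Disagreement between crude and adjusted values is not in itself an error, since the product use categories are self-selected.
3. **Equal weighting is the software default, and the SAP does call the values LS means.** This stands only in part, because the SAP and the table title present them as proportions of subjects, with nothing about balanced levels.
4. **The stakes are small.** The table is secondary, carries no p-values and is not flagged for topline or ClinicalTrials.gov reporting. This stands and sets the grade.

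A reader might also infer more than the documents support:

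- *That the table shows the rate in a population where half coughed at baseline.* It does not. With the worked inputs that rate is 35.0%, not 29.0%, because a back-transformed mean logit is not a mean probability.
- *That the proportions are always too high, or the gap always inflated below 50% baseline cough.* Neither holds, as the 40% row and the second case show.
- *That the MMRM of section 12.7.1.2 is free of the issue.* Only in part. Baseline is continuous there and held at its mean, but sex and Caucasian origin get the same equal weights.

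**Conclusion.** The point holds as a minor correction to one secondary table. Followed exactly, the printed code yields values that do not estimate adjusted cough proportions in FAS-EX, and the SAP describes them as proportions of subjects. That conclusion rests on the printed code and the LSMEANS default alone.

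The size rests on assumed rates. For CC-use the error runs from +14.0 to −6.0 points as baseline cough goes from 10% to 50% under the 60%/10% inputs. Without the FAS-EX prevalence and the cough rates by baseline status, neither sign nor size can be settled from the documents. The odds ratio and its confidence interval stand, so the documents give no ground for inferring that the planned relative comparison of THS-use with CC-use is biased by this weighting.

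**What to change.** In SAP section 12.7.2.5, replace the LS-mean proportions with standardised ones. For each product use category and visit, set every analysed FAS-EX subject to that category, compute the model-predicted probability from the subject's own baseline cough, sex, Caucasian origin, age and smoking intensity, and average over subjects. Give a delta-method or bootstrap 95% CI. Keep the odds ratio as planned.

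Adding OM to the Lsmeans statement is not enough. It corrects the weights but still back-transforms a mean logit, giving 15.8% against 20.0% in the worked case.

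If the default LS means are kept, label them in section 12.7.2.5 and Table 15.2.4.10 as values at balanced covariate levels, not as proportions of FAS-EX subjects.

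The cost is SAP wording, a table label and a few lines of SAS. No new data are needed.
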